4.2.2 Secondary and Exploratory Outcome Variables (if applicable)

The variables used to measure the secondary outcomes will include patient understanding of disease progression, patient understanding of the impact of treatment modalities on disease progression, patient reported pain and functional status, and patient engagement in treatment modalities as measured by the pre- and post-surveys.

4.3 Study Population

The target population for this study will be persons aged 45-65, who have mild to moderate knee pain seeking care from an orthopaedic surgeon specializing in total knee arthroplasty.

4.3.1 Number of Participants

The goal is to screen and accept 200-250 study participants

4.3.2 Eligibility Criteria/Vulnerable Populations

To be included in this study, an individual must be age 45-64 with mild to moderate knee pain consistent with a diagnosis of osteoarthritis. Exclusion criteria includes known inflammatory disease diagnosis (ex. Lupus, Sjogren, or rheumatoid arthritis, prior knee replacement, acute knee trauma), and BMI over 45. This study will not include persons from vulnerable populations.

5 Study Methods/Procedures

[figure not shown]
5.1 Study Procedures

Potential subjects will be identified by the PI and participating orthopaedic surgeons. The PI and Sub-I will recruit potential subjects for this study.

Subjects will be consented in a private room by a designated member of the study team. Each subject will be consented in the language appropriate and presented with a consent form, written in that language. All aspects of the study will be discussed with the potential subject including the reason the subject is being asked to participate, the schedule of visits, the study activities that will occur, and the risks and benefits of participation. The subject will then have an opportunity to ask any questions they have. Once all questions have been answered and the subject feels that he/she would like to participate, the designated member of the research team will obtain verbal consent for the study.

A subject's capacity to provide consent will be evaluated by a member of the consenting staff based on the questions the subject asks about his/her involvement in the study as well as by asking the subject questions pertaining to aspects of the study.

Eligible patients who agree to participate and provide verbal informed consent, will be randomized to participate in either the Control Group or Intervention Group. Both groups will complete the PROMIS Computer Adaptive Test and pre-survey as well as watch a short video providing general information about knee OA. The intervention for the intervention group will be the surgeon utilizing the SDMT during the visit. Both the control and intervention group will complete the post-event survey immediately after completing the control or intervention and then 1 month later.

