The variables used to measure the primary outcome will include patient willingness to proceed with specific treatment modalities as measured by the pre- and post-visit surveys.

Secondary and Exploratory Outcome Variables (if applicable)

The variables used to measure the secondary outcomes will include patient understanding of disease progression, patient understanding of the impact of treatment modalities on disease progression, patient-reported pain and functional status, and patient engagement in treatment modalities as measured by the pre- and post-visit surveys.

Study Population

The target population for this study will be persons aged 45-65, who have mild to moderate knee pain, and are seeking care from an orthopaedic surgeon specializing in total knee arthroplasty.

Number of Participants

We are seeking 200 participants. The attrition rate is assumed to be 10-20%. It may be lower due to the short follow-up period of one month, or higher given the targeted patient demographic. We anticipate enrolling 200-250 patients to account for loss to follow-up.

Study Schedule

We anticipate at least an initial patient visit that would take 30-50 minutes including an explanation of the study and obtaining consent, pre-study survey, PROMIS survey, clinical exam, Shared Decision-Making Tool discussion, and any additional questions the patient may have.

Protocol Revision History

Include the IRB approved protocol version number and date for each revision of the protocol. All version history should remain in the table and never be deleted. The oldest IRB approved version of the protocol should be listed on the top row. The most recent IRB approved version should be listed on the bottom row.

Version Date	Summary of Substantial Changes

Statement of Compliance

This document is a protocol for a human research study. The purpose of this protocol is to ensure that this study is to be conducted according to the Common Rule at 45CFR46 (human subjects) and other applicable government regulations and Institutional research policies and procedures.

Abbreviations

Abbreviation	Explanation
OA	Osteoarthritis
PI	Principal Investigator
SDMT	Shared Decision-Making Tool
UPIRSO	Unanticipated Problems Involving Risks to Subjects or Others

Glossary of Terms

Glossary	Explanation
----------	-------------

Table of Contents

Preface	2
Synopsis	3
Purpose	3
Primary Objective	3
Secondary Objective	3
Study Design	3
Study Date Range and Duration	4
Number of Study Sites	4

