4.2 Outcome Variables

4.2.1 Primary Outcome Variables

The variables used to measure the primary outcome will include patient willingness to proceed with specific treatment modalities as measured by the pre- and post-surveys.

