5.4.2 Sample Size Considerations

We are collecting socioeconomic data, education level, insurance type, pain and activity data at the outset with the thought that these may be related to patient experience or confound the impact of the shared decision-making tool.

PROMIS is standardized, validated tools with defined scoring methods. The three study specific tools (1. SDM Survey; 2. Post-Survey (immediately provided); 3. Post-Survey (One Month Follow-up Survey) would be scored independently using a 5 point scale for each line item. The score of 5 would apply to the most positive score and the score of 1 would apply to the least positive score.

Instrument	Scoring	Comment
Survey (Pre-appointment) (Baseline)	Yes / no or in buckets	Set initial understanding of patient sentiment prior to starting the study
PROMIS	Defined	Knee pain and activity scale
1. SDM Tool	1 to 5 point scale	Primary study outcome
2. Post-appointment Survey Follow-up	1 to 5 point scale	Same as Pre-survey and used to gauge changes in patient sentiment post-study
3. One Month Post-appointment Survey	1 to 5 point scale	Secondary study outcome

Table 2. Items 1 through 3 are the study outcome surveys.

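### Section 5.1 places randomisation before the PROMIS and pre-survey, and nothing says the arm is withheld until these baseline measures are complete

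*Combined protocol and SAP*

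**What the plan says.** The sequence is in Section 5.1. After the consent procedure, patients who have agreed to take part "will be randomized to participate in either the Control Group or Intervention Group. Both groups will complete the PROMIS Computer Adaptive Test and pre-survey"; both groups also watch the same short video. The arms then separate: "The intervention for the intervention group will be the surgeon utilizing the SDMT during the visit".

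The Study Schedule in the Synopsis lists the parts of the visit as "obtaining consent, pre-study survey, PROMIS survey, clinical exam, Shared Decision-Making Tool discussion" but does not place randomisation among them. On consent, Section 5.1 says "All aspects of the study will be discussed with the potential subject including the reason the subject is being asked to participate"; it does not say whether or when the assigned arm is disclosed.

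The baseline values have a stated role. Section 4.2.1 defines the primary outcome variables as "patient willingness to proceed with specific treatment modalities as measured by the pre- and post-surveys", and the Synopsis does the same. Table 2 in Section 5.4.2 labels the pre-appointment survey as baseline, with the comment "Set initial understanding of patient sentiment prior to starting the study". It describes the post-appointment survey as a repeat of the pre-survey, meant to show how sentiment has moved. Section 5.4.2 also says that pain and activity data are gathered at the outset because they may confound the effect of the tool. Section 5.4.3 plans univariate and multivariate regressions without naming the covariates or saying how the pre-survey value is used.

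**The concern.** A baseline value is a safe starting point for change, and a safe covariate, only if the allocation could not have influenced it. Measuring before randomisation guarantees this. Measuring after randomisation relies on nobody who could affect the answers knowing the arm.

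Section 5.1 takes the second route without stating that safeguard. The measures at risk are all self-reported: willingness in the pre-survey, and pain and function in the PROMIS. A patient who has been told that the surgeon will, or will not, go through a decision tool might answer a question about willingness differently. So might a patient handled by staff who know the arm. If that happened, the difference between arms at baseline would no longer be chance alone, and subtracting or adjusting for the baseline would carry part of it into the estimated effect of the tool.

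**Working it through.** **1. Order of steps.**

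| Source | Order given | Randomisation placed? |
|---|---|---|
| Section 5.1 | consent, randomisation, PROMIS and pre-survey and video for both groups, surgeon visit with or without the SDMT, post-survey | after consent, before baseline |
| Synopsis, Study Schedule | consent, pre-study survey, PROMIS, exam, SDMT discussion | no |
| Section 5.4.2, Table 2 | pre-appointment survey is the baseline | no |

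Only Section 5.1 places randomisation, and the people who then complete the baseline measures are already called groups. No readable section places it later.

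**2. Who knows the arm.** No section mentions blinding, masking or concealment, or says when anyone learns the assignment. The surgeon must know it by the visit. Section 5.1 has the participating surgeons help identify candidates, and the PI and sub-investigator recruit them. Nothing states that any of these people, or the patient, is unaware of the arm while the surveys are completed.

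**3. How a shifted baseline would reach the result.** Let b be the shift in mean baseline in one arm caused by knowledge of the arm, and let ρ be the pre-post correlation. Assume equal SDs and no true effect.
- Post-visit values compared without using the baseline: bias from this route = 0.
- Change score: bias = b in size, opposite in sign to the shift.
- Baseline-adjusted regression: bias = ρ × b in size, again opposite in sign.

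Section 5.4.3 does not say which of these will be used.

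**4. Illustration only.** The documents give no value for b or ρ. Assume that pre and post scores share one scale with SD 10 (the SD in Section 5.4.1), 100 patients per arm, and a two-sided test at 0.05. The standard error is 10√(2(1−ρ)) × √(2/100) for a change score and 10√(1−ρ²) × √(2/100) for the adjusted analysis.

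Worked case, b = 2 and ρ = 0.5:
- Change score: SE = 10 × 0.1414 = 1.414; ratio 2/1.414 = 1.414; false-positive rate 0.293.
- Adjusted: SE = 8.660 × 0.1414 = 1.225; bias 0.5 × 2 = 1.0; ratio 0.816; false-positive rate 0.129.

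| b (points) | Change score, ρ 0.3 to 0.7 | Adjusted, ρ 0.3 to 0.7 |
|---|---|---|
| 0 | 0.05 | 0.05 |
| 1 | 0.09 to 0.15 | 0.06 to 0.11 |
| 2 | 0.22 to 0.45 | 0.07 to 0.28 |

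This shows the mechanism and does not estimate this trial's bias. Table 2 scores the pre-survey as yes/no or in categories, so the common scale is itself an assumption.

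**5. The plan's own power statement.** Section 5.4.1 says 200 patients suffice for power 0.8 at a 10% difference with SD 10 points. Taking 10% as 10 points, two-sided 0.05 and 1:1 allocation (none of which is stated), n per arm = 2 × (1.960 + 0.842)² × (10/10)² = 15.7, so 16. With 100 per arm, power exceeds 0.999. The statement reproduces under those assumptions. The timing of randomisation does not enter the formula, so moving it changes nothing here.

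**The case against.** The strongest reply is that the order is inferred from the sequence of two sentences. Section 5.1 has no time marker between them, and the second can be read as listing what the arms share before naming the one difference. A figure placed just before Section 5.1 was not available and may show the flow. Procedures are also identical until the surgeon visit, so patients could be randomised early and still not know their arm at baseline, in which case no harm follows. This stands as a limit on the point: the plan does not show that a bias occurs. It does not remove the point, because no readable text either places randomisation later or withholds the arm.

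A second reply is that the role of the pre-survey in the analysis is undefined, and that Table 2 attaches the primary-outcome label to the SDM Tool instrument. That is fair, and it is why the bias is stated as conditional on a change-score or baseline-adjusted analysis. Section 4.2.1 nevertheless names the pre-survey as part of measuring the primary outcome.

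There are four stronger readings that the documents do not support:
- **That the trial is unblinded.** This would be inferred from silence. Only the surgeon's knowledge, by the time of the visit, is implied.
- **That Table 2 contradicts Section 5.1.** Its comment about the time before the study starts sits beside a pre-appointment label, and the next row uses post-study for the post-appointment survey. A survey after randomisation but before the surgeon visit fits both places.
- **That this order causes extra exclusions.** A patient who leaves on learning the arm before the visit has no post-survey, and is excluded under Section 5.4.6 whichever step came first.
- **That the bias is a given share of the expected effect.** That would need a shift, a correlation and a numerical pre-survey scale, none of which the documents supply.

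**Conclusion.** The point holds as a weakness in the order of steps as written, together with a missing safeguard. It is neither a demonstrated bias nor a numerical error. It rests on reading Section 5.1 in the order in which it is written, and on the absence of any statement about who knows the arm when. Its size cannot be given: it is zero if the arm is already hidden until the surveys are submitted, or if the analysis does not use the baseline. Otherwise it equals the shift (change score) or the correlation times the shift (adjusted analysis). The change is worth making because it removes the risk entirely at no cost.

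**What to change.** Rewrite the sequence in Section 5.1 as: consent; PROMIS; pre-survey; common video; then randomisation, or opening of a concealed assignment, immediately before the surgeon visit. Add a sentence that patient, recruiter and surgeon do not know the arm until the pre-survey has been submitted. Place randomisation explicitly in the Synopsis Study Schedule, and check that the figure before Section 5.1 shows the same order.

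The PROMIS, pre-survey and video are the same in both arms and belong to the same appointment, so this adds no visit, procedure or patient and leaves the sample size and power unchanged. If the clinics already work this way, the change is one sentence of documentation.

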5.1.1 Data Collection

Written survey responses will be collected from patients and electronic responses captured via iPad collection. Each patient will be assigned a random alphanumeric code that will be associated with their survey information. No specific patient identifiers will be recorded along with the survey data. Identifying patient information and research data will be de-identified at the earliest reasonable time after it is received or collected, and a unique study identifier code will be used which does not directly identify the participant. All computers will be password protected and all data will be kept in locked cabinets only accessible by members of the research team. Collaborators will be provided access to data after obtaining permission from the principal investigator.

5.1.2 Adverse Events Definition and Reporting

This protocol presents minimal risks to the subjects and Unanticipated Problems Involving Risks to Subjects or Others (UPIRSOs), including adverse events, are not anticipated. In the unlikely event that such events occur, Reportable Events (which are events that are serious or life-threatening and unanticipated (or anticipated but occurring with a greater frequency than expected) and possibly, probably, or definitely related) or Unanticipated Problems Involving Risks to Subjects or Others that may require a temporary or permanent interruption of study activities will be reported immediately (if possible), followed by a written report within 5 calendar days of the Principal Investigator becoming aware of the event to the IRB (using the appropriate forms from the website) and any appropriate funding and regulatory agencies. The investigator will apprise fellow investigators and study personnel of all UPIRSOs and adverse events that occur during the conduct of this research project via email as they are reviewed by the principal investigator. The protocol's research monitor(s) and regulatory and decision-making bodies will be informed of adverse events within 5 days of the event becoming known to the principal investigator.

Yale will minimize this risk of breach in confidentiality by (a) removing direct identifiers from stored participant information (e.g., names, medical record number); (b) securing any identifiable data in a separate location and limiting access to only those members of the research team listed on the protocol; (c) limiting access to stored information to only those members of the research team listed on the protocol.

5.2 Study Schedule

For this study patients will not need to schedule visits outside of normally requested appointments for care or follow-up. Participation in the study will lengthen the time of a normal visit and is expected to be a 45–50-minute appointment.

5.3 Informed Consent

A waiver of documentation of consent is requested due to the only record linking the subject and the research would be the informed consent form and the principal risk would be potential harm resulting from a breach of confidentiality. Each subject (or legally authorized

representative) will be asked whether the subject wants documentation linking the subject with the research, and the subject's wishes will govern.

5.3.1 Screening (if applicable)

Not applicable

5.3.2 Recruitment, Enrollment and Retention (if applicable)

Potential subjects will be identified by the PI and participating orthopaedic surgeons. PI and Sub-I will recruit potential subjects for this study.

Subject will be consented in a private room by a designated member of the study team listed above. Each subject will be consented in the language appropriate and presented with a consent form, written in that language. All aspects of the study will be discussed with the potential subject including the reason the subject is being asked to participate, the schedule of visits, the study activities that will occur, and the risks and benefits of participation. The subject will then have an opportunity to ask any questions they have. Once all questions have been answered and the subject feels that he/she would like to participate, the designated member of the research team will ask the subject to provide verbal consent.

A subject's capacity to provide consent will be evaluated by a member of the consenting staff based on the questions the subject asks about his/her involvement in the study as well as by asking the subject questions pertaining to aspects of the study.

5.3.3 Study Visits (is applicable)

The only study visit will be the scheduled appointment with the orthopaedic surgery and subsequent meeting with the researcher.

5.4 Statistical Method

5.4.1 Statistical Design

Power Analysis

Statistical Power is determined by the estimated mean and standard deviation of one primary endpoint or composite endpoint to determine ending sample size in each group (test and control). The study power varies with Standard Deviation and Expected Difference in Performance between control and investigational groups. The power is the probability the study will detect a statistical difference between the two groups based on the expected standard deviation and mean difference between the two groups.

This study for which a power of 0.8 is sufficient and we expect a difference in score between the test group and control group to be at least 20% and a standard deviation of 10 points or less. Even if the difference between groups drops to 10% with a standard deviation of 10 points our target sample size of 200 patients is sufficiently powered.

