5.4.3 Planned Analyses

We plan to perform univariate and multivariate regression analyses to assess associations between the SDMT and the patient willingness to proceed with specific treatment modalities. Additional univariate and multivariate regression analyses will be performed to assess our secondary study outcomes.

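### The power claim for a 10% difference assumes an SD of 10 points, which is impossible on the 1-to-5 scale given for the primary outcome instrument; the claim is unsupported there, though not shown false

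*Combined protocol and SAP*

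**What the plan says.** Section 5.4.1 bases power on the mean and SD of "one primary endpoint or composite endpoint to determine ending sample size in each group", sets the target at 0.8, and expects a between-group difference of "at least 20% and a standard deviation of 10 points or less". It then adds a fallback: even if the difference "drops to 10% with a standard deviation of 10 points our target sample size of 200 patients is sufficiently powered". It names no score, no score range, no alpha and no base for either percentage.

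Section 5.4.2 describes the scoring. The study-specific tools "would be scored independently using a 5 point scale for each line item", with 5 the most positive and 1 the least. Table 2 repeats the 1-to-5 scale for its three numbered rows, marks row 1 as the primary study outcome, and notes that "Items 1 through 3 are the study outcome surveys". No section defines a sum, a mean or a 0-100 rescaling, or gives an item count.

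Section 4.2.1 describes the primary outcome as "patient willingness to proceed with specific treatment modalities as measured by the pre- and post-surveys". The Synopsis (Number of Participants) seeks 200, assumes 10-20% attrition and plans to enrol 200-250. Section 5.4.6 excludes patients with missing data.

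**The concern.** The fallback sentence is the plan's only assurance that 200 patients are still enough if the effect is half the size expected. It depends on an SD that the documented scale does not allow, and it sets a percentage without a base against points without a scale. A reader cannot check it. Whether 200 is enough for a 10% difference depends on choices that the plan does not state.

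**Working it through.** **Inputs.** From the documents: power 0.8; differences of 20% and 10%; SD of 10 points or less, then 10 points; 200 patients; two arms; items scored 1 to 5; attrition 10-20%. Assumed, because not stated: two-sided alpha 0.05, 1:1 allocation, unadjusted two-sample t-test, and, for a 1-5 mean, an SD of 0.8 to 1.2. With 200 analysed there are 100 per arm. With 20% attrition from 200 enrolled, 200 × 0.8 = 160, or 80 per arm.

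**1. The plan's own claim.** It cannot be reproduced uniquely. If 10% means 10 points on a 0-100 score, d = 10/10 = 1.0. The t-test then needs 16.7, so 17 per arm, and 100 per arm gives power above 0.999. On that reading the sentence is true, but 200 is not derived from it.

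**2. Largest possible SD.** On a scale from a to b the maximum SD is (b − a)/2, reached with half the scores at each end.
- 1-5 item or item mean: (5 − 1)/2 = 2.
- Change between two such scores (−4 to 4): 8/2 = 4.
- Sum of k items (k to 5k): 4k/2 = 2k, so an SD of 10 needs k ≥ 5.

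**3. Detectable difference.** At 80% power, d = 0.398 with 100 per arm and 0.446 with 80 per arm.

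**4. The 10% case on a 1-5 mean, 100 per arm.** Three bases are possible.

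| Base of 10% | Points | Power at SD 0.8 / 1.0 / 1.2 | Largest SD for 80% power |
|---|---|---|---|
| Mid-scale mean of 3 | 0.3 | 0.75 / 0.56 / 0.42 | 0.3/0.398 = 0.75 |
| Range of 4 | 0.4 | 0.94 / 0.80 / 0.65 | 0.4/0.398 = 1.00 |
| Maximum of 5 | 0.5 | 0.99 / 0.94 / 0.83 | 0.5/0.398 = 1.26 |

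With 80 per arm the rows become 0.65 / 0.47 / 0.35, 0.88 / 0.71 / 0.55 and 0.98 / 0.88 / 0.75.

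**5. The 10% case on a sum of k items with SD 10.** The difference is 0.5k, 0.4k or 0.3k points (10% of maximum, range or mid-scale mean), so d = 0.05k, 0.04k or 0.03k. With 100 per arm, d ≥ 0.398 needs k ≥ 7.96, 9.95 or 13.3, that is 8, 10 or 14 items. With 80 per arm it needs 9, 12 or 15.

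**6. The 20% case on a 1-5 post-visit mean.** The difference is 0.6, 0.8 or 1.0 points. At SD 1.2, power is 0.94, 0.997 and above 0.999 with 100 per arm, and 0.88, 0.99 and above 0.999 with 80 per arm. At the maximum SD of 2 with 100 per arm it is 0.56, 0.80 and 0.94. For a change score at its maximum SD of 4, d = 0.20 for 0.8 points and 0.25 for 1.0 points, and power with 100 per arm is only 0.29 and 0.42.

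**The case against.** The strongest reply is that a 5-point scale per line item describes how items are scored, not what is analysed. Section 5.4.1 allows a composite, and pairing a percentage with points suggests a 0-100 score, on which the sentence holds by a wide margin. This stands as far as it goes: the claim cannot be called false. But the composite appears only in a general description of power. None is chosen or constructed anywhere. PROMIS does not fill the gap either: Table 2 gives its scoring without a range, and section 4.2.2 places pain and function among the secondary outcomes.

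A second reply is that the 20% sentence has the same gaps. That is correct: it too lacks a score, a percentage base and alpha. The difference is that its SD is an upper bound, which admits values possible on a 1-5 scale, whereas the fallback fixes the SD at 10.

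A third reply is that 160 analysed is a worst case. Enrolling 250 with 20% attrition gives 250 × 0.8 = 200, and the Synopsis links attrition to the one-month follow-up, which Table 2 treats as secondary. This also stands, although enrolling only 200 remains within the plan and section 5.4.6 removes incomplete cases.

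A reader might also infer that, after a null result, nobody could tell whether a 10% difference had been missed. That does not follow. The observed confidence interval answers that question, whatever the planning sentence said.

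**Conclusion.** The concern holds in a limited form. The stated power for the 10% case does not fit the 1-5 scale documented for the primary outcome instrument: an SD of 10 is five times the maximum for an item or item mean and two and a half times the maximum for a change score. These bounds need no outside assumption. The power range of 0.42 to 0.99 does. It rests on the assumed SD of 0.8 to 1.2, the three possible bases, two-sided 0.05 and 1:1 allocation.

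A reader might infer that 200 patients are too few. The documents do not support that. They give no SD on the 1-5 scale, and under the assumed SDs the planned 20% difference on a post-visit mean has power of at least 0.94 with 200 analysed and 0.88 with 160.

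The opposite inference, that the 20% case is safe whatever the SD, is not supported either. With 200 analysed, power stays at 0.80 or above up to an SD of 2 only for 0.8 or 1.0 points on a post-visit score. It does not extend to a change score with a large SD.

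This should be fixed, but it is a fault in the justification and not evidence of an underpowered trial.

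**What to change.** In section 5.4.1, name the primary score used for power and restate the calculation in its units. Give its range (and the number of items, if it is a sum), alpha and sidedness, the assumed SD and its source, and the base of the percentage. Do this for the 20% sentence as well.

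Replace the 10%/SD 10 sentence with the detectable difference: about 0.40 SD with 200 analysed and 0.45 SD with 160, for an unadjusted two-group comparison, 1:1, two-sided 0.05. On a 1-5 mean with an SD of 1.0, that is 0.40 and 0.45 points. Say whether 200 means enrolled or analysed. Keep the 10% claim only if it holds on the named score; otherwise delete it and rest the justification on the 20% difference.

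The cost is a few sentences of text and no change in sample size. The downside is that the stated power for the 10% case may become less favourable, or the claim may have to go.
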